5.1.1.2.2 Study periods

- **Screening Period** is defined as any time prior to the date/time of first dose of study drug and after the date/time of the ICF signature. Screening period starts at maximum 28 days prior to the randomization day.
- **Treatment Period** is defined as the period on or after the date/time of the first dose of study drug and ends at the date/time of Week 8 visit or at the date/time the participant has performed the End of Study Visit prior to Week 8. If a participant does not have a Week 8 visit or End of Study Visit, then either the date of the last scheduled or unscheduled visit during the Main Portion or the date of the last known dose of study drug during the Main Portion, whichever is later, will define the end date of Blinded Period.
- **Follow-up Period** starts one day after the Week 8 visit and ends after the final assessments on the safety Follow-up visit (40 days later). For participants who permanently discontinue the study during the treatment period, the follow-up period starts the next day and ends 40 days later after the final safety assessments. Participants with assessments after the blinded period

are considered to have started the Follow-up Period provided, they have not entered the Extension Portion of the study.

- **Extension Period** starts one day after the end of Treatment Period and lasts until the day of the final extension visit.
- **Extension Follow-up Period** starts one day after the end of the final extension visit and ends at the day when final assessments are performed on the safety Follow-up visit (40 days later).

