11.4.1.1 ADVERSE EVENTS

Pre-existing conditions that are detected prior to administration of the first dose of study drug will be recorded as part of the medical history. For all subjects, the AE reporting period will start with the first administration of study drug on Day 1 (for SAE reporting period, see Section 11.4.1.2) and will end 40 days following the last dose of study drug (i.e., the End of Main Visit, Day 57 Visit, or Final Extension Visit), after which no new non-serious AEs are to be reported. The subjects will be monitored throughout the study for any AEs, including clinically significant findings at vital signs measurements, spontaneous reports by study subjects, and observations by the study personnel.

When possible, ongoing AEs assessed as related to the study drug will be followed until resolved or stabilized. Subjects visit the clinic 40 days after their last dose to gather information on ongoing AEs and report any new SAEs since the last study visit (see Section 11.4.1.2 for SAE reporting instructions).

All AEs will be recorded in the eCRF. The investigator will assess and record any AE in detail including the date and time of onset, event diagnosis (if known) or sign/symptom, severity, time course (end date or ongoing), relationship of the AE to study drug, and action(s) taken. All AEs should be reported separately (i.e., 1 record per event).

Reporting of AEs is event-based (i.e., an ongoing event will not be closed until resolved or at the end of study). For the AE description, a diagnosis is preferred over symptoms. If no diagnosis can be made, each symptom will be reported as a separate AE.

Abbreviations should be avoided. Descriptive words should be used for ongoing conditions as applicable (e.g., [REDACTED]).

AEs will be coded using Medical Dictionary for Regulatory Activities (MedDRA; Version 20.0 or higher) after the eCRFs have been monitored and signed by the investigator.

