^a For participants that decide and are eligible to continue in the Extension Portion of the study, the Day 57 visit from the Main Portion will serve as the Day E1 visit and will also include review of eligibility to continue and signing of an informed consent for the Extension Portion.

administered in the same order by the same well-trained evaluator (e.g., neurologist, physical therapist, or other study staff) at each visit throughout the study.

^b If a participant discontinues study drug treatment at any time during the Extension Portion, the participant should return to clinic for a Final Extension Visit.

^c The vital signs assessment will include measurement of HR, body temperature, and blood pressure in the sitting position.

^d During the Extension Portion of the study, all participants should have *Neisseria meningitidis* booster vaccinations as indicated by standard of care. Participants should bring their patient safety card to every study visit. If a participant does not bring the card, then a new one will be given to him/her.

^e All laboratory samples should be obtained after clinical assessments and prior to administration of study drug at applicable visits.

^f Coagulation tests should be performed only in subjects who are receiving anticoagulant therapy.

^g Urine pregnancy tests will be conducted in female subjects of childbearing potential.

^h All AEs and SAEs should be monitored until resolution or stabilization. SAEs that occur within 40 days after the last dose of study drug should be reported using the procedures outlined in the protocol. Participants will attend a clinic visit 40 days after their last dose to gather information on ongoing AEs and report any new SAEs since the last study visit.

ⁱ The clinical assessments should be performed at approximately the same time of day (preferably in the morning) and should be administered in the same order by the same well-trained evaluator (e.g., neurologist, physical therapist, or other study staff) at each visit throughout the study.

^j 3TUG will only be completed in subjects that are ambulatory.

^k Blood samples for PK and PD analysis will be obtained prior to administration of study drug (within 1 hour of dosing).

^l Blood samples for the exploratory tests will be obtained prior to administration of study drug (within 1 hour of dosing).

^m Dosing on study visit days should be held until clinical assessment and blood collection has been completed.

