5.1.1.2.4 Definition of Baseline values

Unless otherwise specified, the Baseline value for the Treatment Period is defined as the most recent (date/time considered) non-missing value obtained prior to the administration of the first study dose. If there are multiple assessments on that day then the time will be considered for the selection of the appropriate measurement. For parameters with no Baseline value as per schedule of assessments the screening value will be set as Baseline value. If a Baseline measurement is not available but an unscheduled measurement occurs after the planned Baseline measurement time point but before dosing, then the unscheduled measurement will be used.

For participants who received placebo in the Treatment Period, the value obtained prior to the first administration of Zilucoplan will occur on the Day E1 (Day 57) visit during the Extension Portion of the study and this will be the Baseline value for them for any summary tables during the Extension Portion of the study. If Day 57 dose is missing the last non-missing dose on placebo during the Main Portion will define the baseline date for the placebo patients who change to active in Extension Portion.

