5.6.2 Adverse Events

Adverse events will be captured from the time of informed consent signature (only the SAEs) or from the time of first administration (Treatment Emergent Adverse Events) and will be reported if occurred during scheduled or unscheduled visits. As Treatment Emergent AE (TEAE) is defined as an AE starting on or after the time of first administration of study drug or an AE that increases in severity after treatment start, if the event was present at the time of the treatment initiation. Reporting of TEAEs refer to the period until the administration of the last study dose plus 40 days (or last visit depending which occurs first).

AEs will be classified according to the Common Terminology Criteria for Adverse Events (CTCAE) Version 5.0 for severity. For any AE where it is not possible to provide a CTCAE grading, the event will be assessed using a standard intensity classification (mild, moderate and severe). For the purpose of the tabulations all CTCAE severity classifications will be mapped to a mild/moderate/severe grade as described below:

- Grade 1 - Mild
- Grade 2 - Moderate
- Grade 3, 4, 5 - Severe

These will be tabulated together with the AEs that were not classified according to CTCAE criteria i.e., all Grade 1 AEs as per CTCAE criteria will be included in the ‘mild’ category together with those AEs classified as mild as per the ‘standard’ intensity classification.

If a particular AE severity is missing, then this will be listed as missing and treated as missing in summaries. If a participant has experienced more than one TEAE within the same PT, then the AE with the greatest severity will be presented. If a participant reported more than one AE within the same (System Organ Class) SOC then the participant will be counted only once with the greatest severity at the SOC where applicable.

Where dates are missing or partially missing, AEs will be assumed to be treatment-emergent unless evidence exists that does not allow the AE to be treatment-emergent. Handling of missing dates for classification of AEs as TEAEs is described in Section 5.1.1.8.

TEAE summaries will be performed in SS and repeated in SS_{NOCOVID-19} if at least 15% of the participants have at least one AE as ‘Confirmed COVID-19’.

Summaries may also be repeated in SS among participants with at least one TEAT based on the COVID-19 period defined as:

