- Before the pandemic: a TEAE will be assigned to this period if the start date of the event is on or after the date of the first administration of study drug on Day 1 but before the cut-off date of 11th MAR 2020.
- During/after the pandemic: a TEAE will be assigned to the during/after the pandemic Period if the start date of the event is on or after the date of the first administration of study drug on Day 1 but after the cut-off date of 11th MAR 2020.

A TEAE will be counted as related to study drug if the response to the question “Relationship to Study Medication” is “Related”. Severe TEAEs are those with CTCAE Grade 3 or above, or those without a CTCAE grading classified as ‘severe’ by the Investigator. If a participant reports the same event with different relationship assessments, then participant will be counted under both related and not related categories.

Adverse events will be presented as “number of participants (percentage of participants) [number of events]”. In this style of output, “[number of events]” will include all cases of an AE including repeat occurrences in individual participants, while “number of participants” will count each participant only once.

TEAE Summaries will be reported separately within the Main Portion and within the Main and Extension Portion of the study and presented by primary system organ class (PSOC) and preferred term (PT) within each IMP. PSOCs will be sorted alphabetically. PTs will be sorted by decreasing frequency of Zilucoplan within each PSOC; ties will be sorted alphabetically within Zilucoplan. TEAEs will be mapped to a study portion based on the onset date.

The following summaries will be produced:

- TEAE overview table in SS and SS_{NOCOVID-19}, displaying participants with at least one TEAE, with at least one TEAE before/after 11th March 2020, with at least one serious TEAE, with at least one TEAE resulting to permanent withdrawal from study medication, with at least one drug-related TEAE and with at least one TEAE leading to death
- TEAEs by PSOC and PT, in SS
- TEAEs by PSOC and PT by COVID-19 period, in SS
- Serious TEAEs by PSOC and PT in SS
- Serious TEAEs by PSOC and PT for each COVID-19 period, in SS
- TEAEs by PSOC, PT and maximum CTCAE V5.0 Grade, in SS
- TEAEs by PSOC, PT and maximum relationship, in SS
- Serious TEAEs by PSOC, PT and maximum relationship, in SS
- Fatal TEAEs by PSOC, PT and maximum relationship, in SS

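### The SAP starts the Extension Period the day after the visit at which it places former-placebo participants' first zilucoplan dose, so first-day reactions are filed under placebo or fall in no period

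*SAP*

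**What the plan says.** **Period boundaries.** Under SAP 5.1.1.2.2 the Treatment Period "ends at the date/time of Week 8 visit", and the Extension Period "starts one day after the end of Treatment Period and lasts until the day of the final extension visit".

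**Day 57 and Day E1.** For participants who continue, "the Day 57 visit from the Main Portion will serve as the Day E1 visit" (SAP Table 1-3, footnote a). On visit days the injection comes last: "Dosing on study visit days should be held until clinical assessment and blood collection has been completed" (footnote m of the same table). For former-placebo participants, SAP 5.1.1.2.4 says that "the value obtained prior to the first administration of Zilucoplan will occur on the Day E1 (Day 57) visit". Protocol Table 2 also marks zilucoplan administration on Day E1.

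**Assignment of events.** SAP 5.6.2 states: "TEAEs will be mapped to a study portion based on the onset date". SAP 5.1.1.8.3 requires one portion, and only one, per TEAE, and sends an event whose portion cannot be determined to the Main Portion. SAP Section 4 places a crossover in the placebo or the zilucoplan group according to the study period being assessed.

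**Exposure.** SAP 5.6.1 splits the exposure of participants who received both treatments by the start and stop dates of each treatment.

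**Worsening.** A TEAE includes "an AE that increases in severity after treatment start, if the event was present at the time of the treatment initiation" (SAP 5.6.2). No second reference point is set at the switch to zilucoplan. Protocol 11.4.1.1 makes reporting event-based: "an ongoing event will not be closed until resolved or at the end of study".

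**The concern.** TEAE incidence is the primary safety endpoint. Injection-site and hypersensitivity reactions are events of interest (SAP 5.6.3), and Protocol 11.3.2 gives injection-site reactions as an example of events strongly associated with drug exposure. The day of first exposure is a natural place to look for them. If that day sits outside the Extension Period for every crossover, an acute reaction to zilucoplan can appear in the placebo column of the Main tables and be missing from the combined zilucoplan tables. The exposure-adjusted incidence rate (EAIR) would then count the day in its denominator but not the event in its numerator. The tables listed in SAP 5.6.2 and 5.6.3 include no separate crossover summary that would bring such events back.

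A second, separate gap concerns events that begin on placebo and become more severe on zilucoplan. They keep a Main onset date, so nothing counts the worsening under zilucoplan.

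**Working it through.** The plan gives no figure on this point, so the check applies its rules to test cases.

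**Inputs**
- Treatment Period ends: Week 8 visit, Day 57 (SAP 5.1.1.2.2).
- Extension Period starts: 57 + 1 = Day 58, i.e. Day E2 (same section).
- First zilucoplan dose of a crossover: Day 57, after the assessments (SAP 5.1.1.2.4; Table 1-3, footnote m; Protocol Table 2).
- Assumed clock times on Day 57: visit at 09:00, dose at 11:00. Any dose time later than the visit time gives the same result.

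**Test cases for a placebo-to-zilucoplan crossover**

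| Event | Mapped by date | Mapped by date and time | Boundary at first zilucoplan dose |
|---|---|---|---|
| Onset Day 57, 1 h after dose | Main / placebo | neither period | Extension / zilucoplan |
| Onset Day 57, 10 h after dose | Main / placebo | neither period | Extension / zilucoplan |
| Onset Day 58 | Extension / zilucoplan | Extension / zilucoplan | Extension / zilucoplan |
| Onset Day 50, worsens Day 70 | Main / placebo | Main / placebo | Main / placebo |

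In the date-and-time column, the event comes after the visit has closed the Treatment Period and before Day 58. If the programmer treats that gap as undeterminable, the default in SAP 5.1.1.8.3 sends it to Main, which again is placebo.

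**Against exposure.** Under SAP 5.6.1 a crossover's zilucoplan time starts on Day 57. The first day is therefore in the EAIR denominator while its events are outside the numerator. With 12 crossovers, that is 12 / 365.25 = 0.033 participant-years. The denominator hardly matters; what matters is any missing event.

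**Reach.** The planned placebo arm is 12, so at most about 12 first-exposure days are affected. In an arm of 12, one participant is 1/12 = 8.3 percentage points of incidence, provided that participant was not already counted in the same table row.

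**Direction.** A zilucoplan-arm participant's Day 57 event is a zilucoplan event in either portion. A crossover's Day 57 event before the dose is correctly placebo. Only a crossover's post-dose event changes column, and only from zilucoplan to placebo.

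**Worsening.** The last row does not respond to the boundary. It follows from onset-date mapping and needs its own rule.

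**The case against.** **The Day 57 drug is not settled.** Protocol 7.2.2 gives the randomized drug through Day 57, Protocol Table 1 marks blinded study drug at Week 8, and SAP Table 1-3 labels its Extension dosing row as either product. If the Day 57 dose were still placebo, first zilucoplan would fall on Day 58 and the boundary would already fit. This stands as a conflict that the documents must resolve. SAP 5.1.1.2.4 and Protocol Table 2 state the opposite.

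**Placebo attribution is not the only reading.** SAP 5.1.1.2.4 speaks of Day E1 as lying in the Extension Portion, while 5.1.1.2.2 defines periods, not portions. The Safety Set is analysed by treatment actually received, and the default to Main is written for ambiguous or incomplete data. This stands in part: misfiling under placebo is the result of date-level mapping, not a certainty. No text, however, expressly assigns a post-dose Day E1 event to zilucoplan.

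**A cancelled safety comparison does not follow.** A reader might infer that half of all first-exposure days (12 of 24) are filed under placebo, so that a first-day reaction rate p gives 12p events in each arm and no difference. The documents do not support this. They give no value of p and no basis for a zero rate on placebo, which is also a daily subcutaneous injection. Protocol 5.4.3 reports no apparent difference in adverse-event pattern or tolerability between zilucoplan and placebo in the earlier myasthenia gravis study. Participants are counted once, so a Day 57 event need not change overall incidence, and not all placebo participants need enter the Extension.

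**Worsening events are not wrongly under placebo.** A reader might infer that they are. An event that began on placebo is correctly a placebo-onset event; what is missing is an additional count under zilucoplan. Even that depends on recording: neither document tells sites to open a new record when severity increases, and neither forbids it.

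**The tables are descriptive.** No safety hypothesis is tested and all adverse events are listed (SAP 5.6.2), so the events remain traceable. This stands, and it limits the severity.

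**Conclusion.** The rule is wrong as written and should be fixed. On the SAP's own placement of the first zilucoplan dose, a post-dose reaction on Day E1 in a former-placebo participant goes to placebo by date, or to no period by date and time, while the same SAP counts that day as zilucoplan exposure. The reach is one calendar day in at most about 12 participants, in descriptive TEAE and EAIR tables. The number of events cannot be derived from the documents; only the direction can, and it is from zilucoplan to placebo. The conclusion assumes that the Day 57 dose of crossovers is zilucoplan and that mapping follows the literal period and onset rules. The gap for worsening events is separate and assumes that sites do not record an increase in severity as a new event.

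**What to change.** 1. In SAP 5.1.1.2.2, for participants who enter the Extension, end the Main Treatment Period and start the Extension Period at the recorded date and time of the first Extension zilucoplan dose.
2. In SAP 5.6.2, map TEAEs by onset date and time against that boundary, and state a rule for Day E1 events with unknown time. Assigning them to the Extension is the more cautious choice for safety. It would be an exception to the default in 5.1.1.8.3 and may count a few pre-dose events under zilucoplan.
3. Reconcile Protocol 7.2.2 and SAP Table 1-3 with SAP 5.1.1.2.4 and Protocol Table 2 on which drug is given on Day 57. A boundary tied to the actual first zilucoplan dose works under either answer.
4. In the zilucoplan tables for former-placebo participants, also count events that began on placebo and increased in severity after the first zilucoplan dose, where the data record the increase. The placebo-onset event stays under placebo.

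The cost is SAP wording and programming. Onset time is already collected (Protocol 11.4.1.1); the study team should confirm that the Day E1 dose time is recorded as well. The change belongs before unblinding, so that no event is moved between columns with treatment known.

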5.1.1.2.3 Mapping of assessments performed at Early Discontinuation Visit

If a participant prematurely discontinues treatment at any time during the Main Portion, then he/she should return to the clinic for a stand-alone End of Main Visit. Corresponding assessments will be mapped to the next visit scheduled where each assessment is done as per protocol.

5.1.1.2.4 Definition of Baseline values

Unless otherwise specified, the Baseline value for the Treatment Period is defined as the most recent (date/time considered) non-missing value obtained prior to the administration of the first study dose. If there are multiple assessments on that day then the time will be considered for the selection of the appropriate measurement. For parameters with no Baseline value as per schedule of assessments the screening value will be set as Baseline value. If a Baseline measurement is not available but an unscheduled measurement occurs after the planned Baseline measurement time point but before dosing, then the unscheduled measurement will be used.

For participants who received placebo in the Treatment Period, the value obtained prior to the first administration of Zilucoplan will occur on the Day E1 (Day 57) visit during the Extension Portion of the study and this will be the Baseline value for them for any summary tables during the Extension Portion of the study. If Day 57 dose is missing the last non-missing dose on placebo during the Main Portion will define the baseline date for the placebo patients who change to active in Extension Portion.

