1.2 Study design

IMNM01 is a multicenter, randomized, double-blind, placebo-controlled parallel study to evaluate the safety, tolerability and efficacy of Zilucoplan in IMNM cases who are positive for anti-HMGCR (3-hydroxy-3-methyl-glutaryl-coenzyme A reductase) or anti-SRP (signal recognition particle) autoantibodies.

The planned enrollment is approximately 24 participants.

Participants are randomized at Day 1 to 1:1 ratio in order to receive:

- daily SC doses of 0.3 mg/kg Zilucoplan (12 participants), or
- matching placebo administered SC (12 participants).

Randomization is stratified based on the antibody status (anti-HMGCR+ versus antiSRP+).

Following in-clinic education and training all participants will self-inject daily SC doses of blinded study drug, according to randomized treatment allocation, for the subsequent 8 weeks. Single use pre-filled syringes in injection devices are provided for use during the study.

All standard of care therapy medications for IMNM should be kept at the same doses throughout the study, including corticosteroids, immunosuppressive drugs, and IVIG.

The study is comprised of the Main Portion and the Extension Portion. The Main Portion of the study includes a Screening Period of up to 4 Weeks and an 8 Week Treatment Period.

During the Treatment Period, participants will return to the clinic at Week 1, Week 2, Week 4 and Week 8 for safety, tolerability and efficacy evaluations.

Efficacy assessments include Creatine Kinase (CK) levels, as well as performance outcomes, clinician-reported outcomes and patient-reported outcomes (PRO).

Safety assessments include physical examination, vital signs, electrocardiogram (ECG), clinical laboratory tests, adverse event (AE) monitoring and immunogenicity.

Additional assessments include biomarker testing, pharmacokinetics, pharmacodynamics, and optional pharmacogenomics.

At the end the study Treatment Period, participants have the option to receive Zilucoplan in the Extension Portion of the study provided they meet the Extension Portion selection criteria. Visits during the first 8 Weeks of the Extension Portion are identical to the Main Portion of the study for all participants to ensure appropriate monitoring of participants transitioning from placebo to active treatment.

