^q The pharmacogenomic sample may be collected at any study visit.

^r Dosing on study visit days should be held until clinical assessment and blood collection has been completed.

Table 1-3: Schedule of Assessments During the Extension Portion of the Study

	Month 2			Month 3	Month 4	Month 5	Month 6	Visits after Day E117			
Study Procedure	Day E1 ^a (Day 57)	Day E8 (±2 days)	Day E15 (±2 days)	Day E29 (±2 days)	Day E57 (±2 days)	Day E87 (±7 days)	Day E117 (±7 days)	Each Month (±7 days)	Every 3 Months (±7 days)	Final Extension Visit ^b	Safety Follow-up Visit (last dose + 40d)
Informed consent	X										
Review eligibility and randomization	X										
Weight	X			X	X		X		X	X	
Prior and concomitant medications	X	X	X	X	X	†	X	X	X	X	X
Safety											
Physical examination	X	X	X	X	†		X		X	X	X
Vital signs ^c	X	X	X	X	X		X		X	X	X
12-lead ECG	X				X				X		
Neisseria meningitidis vaccination ^d	X	Standard of Care	Standard of Care	Standard of Care	Standard of Care	Standard of Care	Standard of Care	Standard of Care			
Hematology / Chemistry / CK ^e	X	X	X	X	X		X		X	X	
Coagulation ^{e,f}	X	X	X	X	X		X		X	X	
Urinalysis ^e	X	X	X	X	X		X		X	X	
Pregnancy test ^g	X	X	X	X	X	X	X	X	X	X	X
Adverse Events ^h	X	X	X	X	X	X	X	X	X	X	X ^h
Anti-Drug Antibody ^e	X	X		X	X		X		X	X	
Efficacy											

Table 1-3: Schedule of Assessments During the Extension Portion of the Study

	Month 2			Month 3	Month 4	Month 5	Month 6	Visits after Day E117			
Study Procedure	Day E1 ^a (Day 57)	Day E8 (±2 days)	Day E15 (±2 days)	Day E29 (±2 days)	Day E57 (±2 days)	Day E87 (±7 days)	Day E117 (±7 days)	Each Month (±7 days)	Every 3 Months (±7 days)	Final Extension Visit ^b	Safety Follow-up Visit (last dose + 40d)
3TUG ^{i,j}	X			X	X		X		X	X	
Proximal MMT ⁱ	X			X	X		X		X	X	
Physician Global Activity VAS ⁱ	X			X	X		X		X	X	
Patient Global Activity VAS ⁱ	X			X	X		X		X	X	
HAQ ⁱ	X			X	X		X		X	X	
MDAAT ⁱ	X			X	X		X		X	X	
FACIT-Fatigue ⁱ	X			X	X		X		X	X	
Pharmacokinetic / Pharmacodynamic											
Zilucoplan plasma PK ^k	X	X	X	X	X		X		X	X	
Pharmacodynamic analysis ^k	X	X	X	X	X		X		X	X	
Exploratory											
Autoantibodies testing	X			X	X		X		X	X	
Biomarker testing ^l	X	X	X	X	X		X		X	X	
Study Drug											
Zilucoplan or placebo administration ^m	X	X	X	X	X	X	X	X	X	X	

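### SAP 5.1.1.2.4 gives former-placebo participants two conflicting Extension baseline rules when the Day 57 dose is missing; taken literally, the second places pre-zilucoplan Day 57 values after baseline

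*SAP*

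**What the plan says.** SAP 5.1.1.2.4 (Definition of Baseline values) contains three relevant rules.

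- **Treatment Period, general rule:** baseline is "the most recent (date/time considered) non-missing value obtained prior to the administration of the first study dose".
- **Extension, former-placebo participants:** "the value obtained prior to the first administration of Zilucoplan will occur on the Day E1 (Day 57) visit during the Extension Portion", and "this will be the Baseline value for them for any summary tables during the Extension Portion of the study".
- **Fallback for the same participants:** "If Day 57 dose is missing the last non-missing dose on placebo during the Main Portion will define the baseline date".

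Three features of the schedule in SAP 1.2 bear on the fallback.

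- Dosing is daily: "all participants will self-inject daily SC doses of blinded study drug".
- Main Portion visits are sparse: "participants will return to the clinic at Week 1, Week 2, Week 4 and Week 8".
- At visits, assessment comes before dosing: "Dosing on study visit days should be held until clinical assessment and blood collection has been completed".

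SAP 5.1.1.4 displays Extension efficacy separately for the placebo-to-zilucoplan group. SAP 5.5.1 makes the long-term efficacy analysis descriptive, with no statistical comparison.

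**The concern.** The second rule anchors baseline to the start of zilucoplan. The fallback anchors it to the end of placebo. They agree when the participant is dosed on schedule and diverge when the Day 57 dose is missing.

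A participant can attend Day 57, be assessed and bled, and then not be dosed. Those Day 57 values precede any zilucoplan and are the natural pre-drug reference. Under the fallback, the baseline date is the last placebo dose, normally the day before, so the Day 57 values come after it. An older value would serve as baseline, and whatever happened on placebo in between would be reported as change on zilucoplan. The error can run either way, because improvement and worsening on placebo are misattributed alike.

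**Working it through.** The plan gives no figure to reproduce here. The check applies the fallback literally to the visit schedule.

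**Inputs**
- Day 29 window ±2 days, Day 57 window ±7 days (Protocol Table 1, SAP Table 1–2).
- Main Portion assessments (same tables): CK and other laboratory tests and vital signs at Screening, Days 1, 8, 15, 29 and 57; clinical scales at Screening, Days 1, 29 and 57; ECG at Screening and Day 57 only.
- Planned placebo group: 12 (SAP 1.2).
- Change from baseline = post-baseline value − baseline value (SAP 5.1).

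**Step 1: baseline date.** With daily dosing and no other missed dose, the last placebo dose is nominally Day 56. Any last dose from Day 30 to Day 56 gives the same result below.

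**Step 2: from date to value.** The SAP does not define this step. By analogy with the section's general rule, I take the most recent non-missing scheduled value on or before that date.

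| Parameter | Value used as baseline |
|---|---|
| CK, other laboratory tests, vital signs | Week 4 (Day 29) |
| 3TUG, MMT, both global VAS, HAQ, MDAAT, FACIT-Fatigue | Week 4 (Day 29) |
| ECG | Screening |

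An unscheduled value after Week 4 and up to the last placebo dose would take precedence.

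**Step 3: age of that baseline relative to Day 57.**
- Week 4, nominal: 57 − 29 = 28 days.
- Shortest within the windows: 50 − 31 = 19 days. Longest: 64 − 27 = 37 days.
- ECG, with Day 57 at its nominal date and no relative Day 0 (SAP 5.1.1.2.1): 1 + 56 = 57 days from Day −1, up to 28 + 56 = 84 days from Day −28.

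**Step 4: effect on the reported change.** Reported Extension change = (Extension value − Day 57 value) + (Day 57 value − Week 4 value). The second bracket arose on placebo. It stays in the total even if Day 57 itself is not shown as an Extension visit.

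*Illustration with assumed values, Physician Global VAS:* 6.0 at Week 4, 4.0 on Day 57, 4.0 on Day E57.
- From Day 57: 4.0 − 4.0 = 0.
- From Week 4: 4.0 − 6.0 = −2.0.
- Shift in the mean of a 12-person group from this one participant: −2.0 / 12 = −0.17 on a 10 cm scale.

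*Illustration with assumed values, CK:* 3000 at Week 4, 2000 on Day 57, 1000 later.
- From Day 57: 100 × (1000 − 2000) / 2000 = −50.0%.
- From Week 4: 100 × (1000 − 3000) / 3000 = −66.7%.
- Change on placebo: 100 × (2000 − 3000) / 3000 = −33.3%.

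**Step 5: reach.** One participant carries at least 1/12 = 8.3% of a group mean, and more if fewer than 12 enter the Extension.

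**Step 6: under the replacement rule.** Taking the last non-missing value before the first zilucoplan administration keeps the Day 57 value as baseline for every parameter measured that day, whether or not the Day 57 dose is taken.

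**The case against.** **The SAP never says that a Week 4 value replaces Day 57.** The fallback speaks of a baseline date, while the sentence before it fixes the baseline value as "the value obtained prior to the first administration of Zilucoplan will occur on the Day E1 (Day 57) visit", and nothing cancels that expressly. This stands: the step from date to value is an inference, and the defect is a conflict between two sentences rather than an explicit instruction to use Week 4.

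**Dose may have been meant as data.** Elsewhere (SAP 5.6.1 and 6.1.8) the SAP calls untaken doses missed, whereas missing and non-missing are its usual words for absent data. Read as absent Day 57 data, for instance after a remote COVID-19 visit (Protocol 7.4), falling back to the last value on placebo would be correct. This is possible, but the sentence says dose, and a programmer will implement what is written. The replacement wording gives the right result under either reading.

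**The trigger is narrow.** The participant must complete the Main Portion, enter the Extension, be assessed on Day 57 and yet receive no dose, although Protocol 9.1.2 has injections at visits supervised. This stands, and the documents give no rate for it. The SAP nevertheless wrote a rule for the case.

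**It is unclear whether the Day 57 dose is placebo or zilucoplan.** Protocol 7.2.2 runs randomised treatment to Day 57, while Protocol Table 2 lists zilucoplan at Day E1. The problem arises under both readings.

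**Conclusion.** The point holds as a minor defect: two adjacent sentences conflict, and the literal fallback gives a wrong Extension baseline when Day 57 values exist but the Day 57 dose is missing. The size rests on the assumption in Step 2 and on there being no unscheduled value. It is confined to baseline-dependent, descriptive Extension summaries in the placebo-to-zilucoplan group, and within it to those who miss that dose.

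A reader might infer more than the documents support.

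- **That the Week 8 results are at risk.** They are not. The primary and secondary analyses use the Treatment Period baseline.
- **That every Extension summary is affected.** Several laboratory criteria in SAP Table 6–3 (for example hemoglobin, platelets, potassium and sodium) are absolute thresholds, and adverse event rates use exposure dates.
- **That the pre-drug value is lost.** Day 57 is also the Week 8 Main Portion value, and laboratory, vital sign and ECG results are listed by participant.
- **That the baseline is always at least four weeks too old.** The visit windows allow 19 days.

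**What to change.** Replace the fallback sentence in SAP 5.1.1.2.4 with:

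> For participants randomised to placebo, the Extension baseline is the last non-missing value before the first actual administration of zilucoplan, whatever the date of that dose; Day 57 assessments are used when they precede it.

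This follows the principle of the preceding sentence, mirrors the Treatment Period rule, and also covers absent Day 57 data. Nothing changes for participants dosed and assessed on schedule. The cost is one sentence in the SAP and the matching line in the programming specification; no new data are needed.
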